Study Title: Comparison between angled-tip and straight-tip guidewire in biliary cannulation: A prospective, randomized trial
Protocol Version Number: Version 1.0 Protocol Date: 08/29/2022

Title Page:

Comparison between an angled-tip and straight-tip guidewire in biliary cannulation: a prospective, randomized trial

Principle Investigator:

[name] MD

Program Director, Advanced Endoscopy Fellowship

Director of Advanced Endoscopy

Clinical Associate Professor of Medicine, Tufts University School of Medicine

Division of Gastroenterology and Hepatology

Lahey Hospital and Medical Center

Sub-Investigators:

[name] MD

Advanced Endoscopy Fellow

Division of Gastroenterology and Hepatology

Lahey Hospital and Medical Center

Table of Contents

- **Research Objectives/Specific Aims/Outcomes Measures**
- **Background Information/Significance/Scientific Rationale**
- **Participant Selection/Eligibility**
- **Subject Enrollment**
- **Study Design/Procedures**
- **Study Calendar/Schematic/Schedule**
- **Potential Risks/Discomforts**
- **Potential Benefits**
- **Statistical Analysis**
- **Data Management**
- **Data and Safety Monitoring and Quality Assurance**
- **References**

Study Title: Comparison between angled-tip and straight-tip guidewire in biliary cannulation: A prospective, randomized trial

Protocol Version Number: Version 1.0 Protocol Date: 08/29/2022

Research Objectives/Specific Aims/Outcomes Measures

Wire-guided cannulation of the common bile duct is a standard technique utilized during Endoscopic Retrograde Cholangio-Pancreatography (ERCP) to ensure safe and effective access to the common bile duct via the ampulla of Vater. Due to the anatomy of the ampulla, and the orientation of the biliary orifice, a guidewire with an angled tip may allow easier and safer access to the common bile duct without inadvertent manipulation of the pancreatic duct. We aim to assess the technical and clinical outcomes between an angled-tip guidewire (GW) compared to a straight-tip guidewire in wire-guided cannulation of the common bile duct. We hypothesize that an angled-tip GW is associated with increased rate of successful cannulation, decreased procedure time and decreased rate of post-ERCP pancreatitis in wire-guided biliary cannulation during ERCP.

Primary Research Question:

Is the use of an angled-tip guidewire associated with increased rate of successful cannulation of the common bile duct in ERCP?

Secondary Research Questions:

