This is a prospective, randomized, unblinded trial performed at Lahey Hospital and Medical Center. All procedures will be performed by experienced advanced endoscopists with over 2000 career ERCP's and 350 ERCP's performed per year, (or by the advanced endoscopy fellow under supervision of the attending gastroenterologist). Enrolled patients will be randomly assigned by a computer-generated number list to 2 groups (group 1, angled-tip GW; group 2, straight-tip GW). All procedures will be performed using standard duodenoscope or Exalt duodenoscope (JF-260V; Olympus Medical Systems Corp, Tokyo, Japan). For the procedure, patients will receive either general anesthesia or monitored anesthesia care as clinically indicated. Medications will be administered by a licensed anesthesiologist or CRNA. All procedures will be performed via short-wire technique using a 0.025-inch, 260cm-long angled guidewire with 5-cm hydrophilic tip (Jagwire Revolution, Boston Scientific, Natick, MA) or a 0.025-inch, 260-cm long straight guidewire with a 5-cm hydrophilic tip. (Jagwire, Boston Scientific, Natick, MA) For cannulation, attending gastroenterologists will be allowed 5 minutes to cannulate (from first contact of ampulla) or 5 passes inadvertently into the pancreatic duct (whichever occurs first). If the procedure is performed by gastroenterology fellow, the fellow will be allowed 5 minutes from first contact with the ampulla or 5 passes into the pancreatic duct (whichever occurs first). If the pancreatic duct is cannulated, double guide-wire technique will be performed with the same wire (0.025-inch guidewire) for an additional 5 minutes. If cannulation remains unsuccessful, needle-knife technique will be performed with pancreatic duct stenting performed. This protocol is similar to Vihervaara et al.² Post-procedurally, patients will be monitored for post-ERCP pancreatitis with either inpatient follow-up or via a phone call if procedure performed as outpatient. Post-ERCP pancreatitis will be defined as new or worsened abdominal pain combined with >3 times the normal value of lipase more than 24 hours after ERCP and requirement of hospital admission or prolongation of a planned admission. Routine blood work will be collected upon admission and during hospitalization as clinically warranted. Data will be collected using the REDCap data collection application and will be securely stored on LHMC secured servers.

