Study Title: Comparison between angled-tip and straight-tip guidewire in biliary cannulation: A prospective, randomized trial

Protocol Version Number: Version 1.0 Protocol Date: 08/29/2022

Standard of Care: Procedure in both treatment groups is considered standard of care as they use FDA approved devices. Here at Lahey, The endoscopists use both guidewires. The guidewire is selected based on physician preference. While they typically start with a straight-tip wire, they would also use angled-tip guidewire if the straight tip guidewire does not achieve cannulation of the bile duct. Data shows that both guidewires are safe to use with similar rates of successful cannulation and adverse events.

Study Calendar / Schematic / Schedule

The main study-required visit will be the day of the planned procedure (ERCP). On this visit, the pre-procedural process will include a discussion with the patient regarding the risks and benefits of the procedure as well as a description of the study and consent for participation in the study. Pre-procedure data will be collected and entered into the data capture tool. The data collected will include patient demographics and indication for procedure. Randomization will then be performed immediately prior to the start of the planned procedure and the randomization assignment will be entered into the data capture tool. Data will then be collected immediately after the procedure and will include procedure duration, successful cannulation determination, pancreatic duct cannulation determination, types of guidewires used during procedure, fellows involvement in procedure and complications of procedure. On post-procedure day one to post procedure day five, post-procedural data will be collected by either inpatient assessment or by a telephone call to the subject if the procedure was performed on an outpatient basis by either the PI or sub-investigators. If there is a concern for possible post-ERCP pancreatitis, a lipase level will be checked on an inpatient or outpatient basis. There will be no other planned study-required visits after post-procedure day five. Subjects will be removed from enrollment if they choose to withdraw from the study.

Potential Risks and Discomforts

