The sample size needed to achieve statistical significance for the primary outcome is 248 (207 *1.2) after adding 20% screen failure rate. The power of the study to detect if there is a true difference will be 0.80. It will take approximately six months to reach the target accrual. The variables that need to be collected include demographics, co-morbidities, laboratory values, date of procedure, diagnosis, outcome of procedure (success of cannulation), duration of procedure, post-procedure complications (including post-ERCP pancreatitis) and fellow involvement in procedure. The outcome variables include rate of successful cannulation, and incidence of post-ERCP pancreatitis. Predictor variables include co-morbidities, indication for procedure and fellow involvement in procedure. Potential confounding variables include differing anatomy of papilla amongst subjects, underlying etiology of biliary obstruction (which may be different from suspected pre-procedure diagnosis) or unforeseen biliary pathology which alters procedure. The study endpoints will be achieved by showing a statistically significant difference in the rate of successful cannulation using an angled-wire as compared to a straight wire as defined as a p-value of less than 0.05. The proportion of procedures that are successful in the two treatment arms will be compared using chi squared analysis. Similarly, the rate of development of pancreatitis will be compared using chi squared analysis. The total duration of the procedure will be compared using a T-Test for comparing mean if the data are normally distributed or a Wilcoxon rank sum test if not normally distributed.

Data Management

All data will be collected using the REDCap Data Collection application and will be stored electronically on this platform. Only the PI and sub-investigators will have access to the password encrypted REDCap database. There will be no transmission of the acquired data off site. The data set will not include patient names or other identifiers. Information for this study will be available as required to the FDA, Massachusetts Department of Health, and LHMC IRB. Names of subjects will not be mentioned in publications or case reports.

Study Title: Comparison between angled-tip and straight-tip guidewire in biliary cannulation: A prospective, randomized trial
Protocol Version Number: Version 1.0 Protocol Date: 08/29/2022

Data and Safety Monitoring and Quality Assurance

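### The primary outcome, successful cannulation, is not tied to a time limit, technique or assigned wire; if later-step or switched-wire entries count, the comparison of tip shapes is diluted

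*Combined protocol and SAP*

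**What the plan says.** The Primary Research Question is: "Is the use of an angled-tip guidewire associated with increased rate of successful cannulation of the common bile duct in ERCP". It names no time limit, technique or wire rule.

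The Statistical Analysis section describes the outcome in two ways:

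- The endpoint sentence refers to the "rate of successful cannulation using an angled-wire as compared to a straight wire".
- The test sentence reads "The proportion of procedures that are successful in the two treatment arms will be compared using chi squared analysis".

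Study Design and Procedures sets out a sequence. In the first attempt, "attending gastroenterologists will be allowed 5 minutes to cannulate (from first contact of ampulla) or 5 passes inadvertently into the pancreatic duct", whichever comes first; a fellow is given the same limit. If the pancreatic duct is entered, a double-wire step follows for 5 more minutes, to be done with the same 0.025-inch wire. Then: "If cannulation remains unsuccessful, needle-knife technique will be performed with pancreatic duct stenting performed". The section does not say which of these steps count towards the primary outcome.

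The Standard of Care paragraph describes site custom. Endoscopists usually start with a straight tip, and "they would also use angled-tip guidewire if the straight tip guidewire does not achieve cannulation of the bile duct".

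The Study Calendar section says: "Data will then be collected immediately after the procedure and will include procedure duration, successful cannulation determination". The types of wire used are also on that list. The step at which the duct was entered is not.

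**The concern.** Randomisation assigns a wire, and tip shape is tested most directly in the first wire-guided attempt. Later steps bring in other techniques that are the same in both arms, so entries gained there raise both success rates and narrow the gap between them. A straight-arm patient whose duct is opened after a change to the angled wire would, if counted as a success, credit the comparator with the test device. Both routes make a finding of no difference more likely even if the angled tip works better.

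There is a second risk. The trial is unblinded and the outcome wording allows more than one reading. Without a written rule, the classification of later-step entries could be settled after results are known. Because the step of entry is not a listed data item, it may also be impossible to reconstruct.

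**Working it through.** **The plan's own figure.** 207 × 1.2 = 248.4, which matches the stated 248. The 207 itself cannot be reproduced, because the plan states no success rates and no target difference. It also cannot show which definition of success was intended, since many pairs of rates fit it. At 80% power and two-sided 0.05 (sidedness is my assumption), 50% vs 69%, 60% vs 78% and 66% vs 83% each need 206 to 208 patients without continuity correction. With the correction, 77% vs 92% and 80% vs 94% each need 208.

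**How much room 207 leaves.** With 207 analysed and 80% power (normal approximation), the detectable difference is about 16 points from a control rate of 70%, 13 points from 80% and 9 points from 90%. From a control rate of 93% upward, even near-100% success in the other arm does not reach 80% power. The definition therefore matters, because counting later entries moves both arms towards that ceiling.

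**Dilution.** Let p be first-attempt success and r the share of first-attempt failures rescued later, equal in both arms. Overall success is q = p + (1 − p)r, so the difference becomes (p₂ − p₁)(1 − r). For example, with p = 0.75 and 0.90 and r = 0.50:

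- straight: 0.75 + 0.25 × 0.50 = 0.875
- angled: 0.90 + 0.10 × 0.50 = 0.95
- difference: 0.075 = 0.15 × 0.50

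Power below comes from exact binomial enumeration of the uncorrected Pearson chi-squared test at two-sided 0.05. It uses 104 straight and 103 angled patients (207 split 1:1). The values of p and r are assumptions.

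| r | Straight | Angled | Difference | Power |
|---|---|---|---|---|
| 0 | 75.0% | 90.0% | 15.0 points | 83% |
| 10% | 77.5% | 91.0% | 13.5 points | 78% |
| 30% | 82.5% | 93.0% | 10.5 points | 65% |
| 50% | 87.5% | 95.0% | 7.5 points | 49% |
| 70% | 92.5% | 97.0% | 4.5 points | 29% |
| 80% | 95.0% | 98.0% | 3.0 points | 19.5% |

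**Other starting rates.** Using the normal approximation and a first-attempt effect set to give 80% power at 207, 70% vs 86% falls to 65% power at r = 25%, 45% at r = 50% and 24% at r = 75%. Regaining 80% power would need about 476 patients at r = 50% and 1,014 at r = 75%. Starting from 60% or 80% in the control arm, power at r = 50% is 43% or 47%.

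**Switched wire.** Suppose half of the straight-arm failures are opened after a change to the angled wire and are counted for the straight arm. The straight rate becomes 0.75 + 0.25 × 0.50 = 0.875 against 0.90, and power is 9%. This is an extreme case, because it gives angled-arm failures no rescue at all.

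**The case against.** A reader might infer that the plan defines the primary outcome as success of the whole procedure, so that rescued entries definitely count. The documents do not go that far:

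- The endpoint sentence, with its "rate of successful cannulation using an angled-wire as compared to a straight wire", points towards success with the assigned wire.
- The list of variables glosses the outcome of the procedure as success of cannulation, so the word procedures in the test sentence may only name the unit of analysis.
- The condition that triggers needle-knife is a clinical step. At most it implies that a double-wire entry is a cannulation; it does not say how an entry after needle-knife is scored.
- Recording the result just after the procedure describes when data are entered. It does not define success.

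Two further points stand. The double-wire step uses the same wire, so if that means the assigned wire, tip shape is still partly under test and counting such entries can be defended. Switching appears only as usual site practice and is not a step in the trial sequence.

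The power figures rest on assumed rates. At a rescue rate of 10% the loss is small. Procedure duration is also compared and might show some benefit of faster entry, although total duration is an imprecise measure of it.

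None of this supplies the missing definition. Later-step entries are not excluded, switching is neither barred nor given an analysis rule, and the recorded wire types have no stated use.

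**Conclusion.** The primary outcome is undefined as to time limit, technique and assigned wire, and this should be corrected before the trial's results are analysed. The Statistical Analysis section supports two readings. Under the one that counts later entries, the first-attempt difference shrinks by the factor (1 − r).

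On the assumed 75% versus 90% with 207 analysed, power falls from 83% to between 78% and about 20% as r rises from 10% to 80%. The pattern is similar from other starting rates. The size for this trial is unknown, because the documents give neither first-attempt nor rescue rates. Crossover to the angled wire could dilute the contrast further, but its frequency under the protocol is also unknown.

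It would be too strong to say that rescue masks any effect of tip shape. Equal rescue below 100% attenuates the difference without erasing it, and the 9% figure is a one-arm worst case.

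**What to change.** **Primary outcome.** Define success as biliary cannulation with the assigned wire within the standard attempt already set in Study Design and Procedures (5 minutes from first contact, or 5 pancreatic passes). For this endpoint, count entries after needle-knife, a change of wire or a change of operator as failures.

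**Double-wire entries.** State their classification explicitly. Because this step uses the same wire, report success including it as a named secondary or sensitivity outcome.

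**Data.** Add a REDCap field for the step and the wire at which the duct was entered.

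**Analysis.** Analyse every randomised patient in the assigned arm. Report final success after any technique as a secondary outcome.

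**Sample size.** State the success rates behind 207 for the definition chosen.

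**Consistency.** Reconcile the same-wire instruction in Study Design and Procedures with the switching custom in the Standard of Care paragraph. This is a request for clarity only; no change to care is proposed.

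**Cost.** Protocol wording and one extra data field. Reported primary success rates will be lower than overall procedural success, so the secondary result should be shown beside them.

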Is the use of an angled-tip guidewire associated with decreased procedure duration?

Is the use of an angled-tip guidewire associated with reduced rates of post-ERCP pancreatitis?

Is cannulation more successful using an angled-tip wire in a particular type of papilla?

Background Information / Significance / Scientific Rationale

Endoscopic Retrograde Cholangio-pancreatography is a commonly performed procedure for diagnostic and therapeutic purposes in the setting of biliary tract pathology. During ERCP, bile duct access is performed with use of a catheter (sphincterotome) that is passed beyond the papilla into the bile duct. The utilization of a guidewire, over which the catheter is passed, to ensure selective common bile duct cannulation (as opposed to pancreatic duct cannulation) is associated with improved overall cannulation rates and lower risks of post-ERCP pancreatitis, and this practice has become standard.¹ A variety of guidewires are available to the endoscopist. The guidewires vary in size, stiffness and design of the tip of the wire, which may be straight, angled, J-shaped or tapered. Angled-tip guidewires were shown to result in decreased procedure duration, with a similar rate of cannulation and complications as compared to a straight tipped wire in a randomized-controlled trial including 239 patients.² Aside from this RCT, there is a paucity of literature that compares angled-tip and straight tip-guidewires in

Study Title: Comparison between angled-tip and straight-tip guidewire in biliary cannulation: A prospective, randomized trial

Protocol Version Number: Version 1.0 Protocol Date: 08/29/2022

biliary cannulation. In theory, an angled-tip guidewire may result in better technical performance including rate of successful cannulation, duration of procedure, and incidence of post-ERCP pancreatitis because of the anatomy of the ampulla of Vater and the oblique trajectory of the biliary orifice. Our goal is to compare the rate of successful cannulation, duration of procedure and incidence of post-ERCP pancreatitis between an angled-tip guidewire and straight-tip guidewire. This study will aid in the performance of ERCP and in the proper selection of devices to ensure safe and effective biliary cannulation. Additionally, this research may reduce healthcare expenditure by identifying an alternative device that may reduce the duration of the ERCP procedure.

Participant Selection / Eligibility

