Patients undergoing ERCP with native papilla and pancreatobiliary disease who are candidates for ERCP with biliary cannulation are eligible for enrollment. Subjects must meet all inclusion criteria in order to be eligible to participate in the study.

Inclusion Criteria:

Patients undergoing ERCP for cholangiography, bile or tissue sampling from the gallbladder or bile duct, or for treatment of biliary diseases (removal of common bile duct stones, biliary stent placement)

Exclusion Criteria:

Patients who are less than 18 years old

Pregnant patients

Patients who have undergone previous bile duct cannulation or sphincterotomy

Patients who have undergone prior endoscopic balloon dilation or needle-knife fistulotomy

Patients who have undergone gastric surgery (Billroth gastrectomy II, Roux-en-Y gastric bypass)

Patients with acute pancreatitis

Patients who refuse endoscopic intervention

Patients with ampullary tumor, duodenal stenosis, or pre-operatively proven pancreaticobiliary malunion

Subjects will be recruited based upon their need to undergo ERCP for biliary diagnosis or therapy as determined by the principal investigator or sub-investigators. This determination will be made based upon the clinical requirement of endoscopic biliary cannulation. Subjects will be either inpatients or outpatients who require ERCP and bile duct cannulation. The overall sample size will be approximately 248 patients. Pregnant women will not be recruited for participation in this study as ERCP in certain pregnancies may be harmful to the fetus especially during the first trimester. Additionally, minors (age less than 18 years old) and prisoners will not be recruited or enrolled in the study, as these are vulnerable populations who may have a compromised ability to make an informed decision about participation.

Study Title: Comparison between angled-tip and straight-tip guidewire in biliary cannulation: A prospective, randomized trial

Protocol Version Number: Version 1.0 Protocol Date: 08/29/2022

Subject Enrollment

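### The duration test is picked by an unspecified normality check on the trial data, with no effect estimate planned and baseline indication unused

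*Combined protocol and SAP*

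**What the plan says.** Duration is the first of the secondary research questions: "Is the use of an angled-tip guidewire associated with decreased procedure duration". The Background section gives it practical weight, saying that "this research may reduce healthcare expenditure by identifying an alternative device that may reduce the duration of the ERCP procedure".

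The only analysis given is in the Statistical Analysis section, where total duration is to be "compared using a T-Test for comparing mean if the data are normally distributed or a Wilcoxon rank sum test if not normally distributed". That section names no test, plot or threshold for normality. For duration it also names no effect measure, confidence interval, covariate, target difference, standard deviation or power. Its list of outcomes leaves duration out: "The outcome variables include rate of successful cannulation, and incidence of post-ERCP pancreatitis".

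On covariates, the Study Calendar section says of the data taken before randomisation: "The data collected will include patient demographics and indication for procedure". The Statistical Analysis section adds: "Predictor variables include co-morbidities, indication for procedure and fellow involvement in procedure". No adjusted or stratified analysis is attached to these variables for any outcome.

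**The concern.** There are three linked gaps.

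- **The test depends on the data.** It is settled only after the durations are seen, in a trial described as unblinded, by investigators who alone have database access, and with no criterion to bind them.
- **The two branches are not interchangeable.** A t-test compares mean minutes. A rank sum test asks whether times in one arm tend to be longer than in the other. A rank p-value with no estimate beside it cannot say how much time was saved, which is what the remark about expenditure needs.
- **A baseline variable goes unused.** Eligible procedures run from cholangiography and sampling to therapy ("or for treatment of biliary diseases (removal of common bile duct stones, biliary stent placement"), so it is plausible that indication accounts for some of the variation in duration.

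The Background section reports that the earlier randomised trial of 239 patients found shorter procedures but similar cannulation and complication rates. Duration is therefore the outcome with prior support, and a clear estimate of it is worth having.

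**Working it through.** **Inputs from the documents.** Statistical Analysis gives 207 patients before inflation and 248 after. The inflation reproduces: 207 × 1.2 = 248.4, or 248. Allocation is 1:1 (Subject Enrollment). The significance level is stated for the primary outcome ("as defined as a p-value of less than 0.05"). Sidedness is not stated, so two-sided 0.05 is assumed. The plan has no figure for duration to reproduce.

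**Assumptions.** Durations are log-normal with log-SD 0.5 unless stated. Normality is judged by Shapiro-Wilk at 0.05 on residuals. The share of variance in log duration explained by indication, R², is taken from 5% to 40%. None of these is in the documents.

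**Step 1: which test is selected.** In simulations with 207 patients (3,000 trials per scenario), Wilcoxon was selected as follows.

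| Log-SD | Wilcoxon selected |
|---|---|
| 0.1 | 32–34% |
| 0.15 | 61–62% |
| 0.2 | 86% |
| 0.3 or more | over 99% |

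With mild skew, chance largely decides the test. With marked skew the rule nearly always ends at Wilcoxon.

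**Step 2: whether the branches differ.** With equal mean minutes but different spread (log-SD 0.4 and 0.7), the t-test rejected in 5% of trials and Wilcoxon in 51%. With a location shift of 0.39 log-SD, the two disagreed on significance in about 6% of trials at log-SD 0.1 to 0.2, 11% at 0.5 and 17% at 0.7.

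**Step 3: type I error of the rule as written.** With identical distributions in both arms, the two-stage rule rejected in 4.5% to 5.4% of trials, so there is no inflation.

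**Step 4: power with and without indication.** A 15% shorter time is a log difference of −ln(0.85) = 0.1625. With arms of 103 and 104:

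SE = 0.5 × √(1 − R²) × √(1/103 + 1/104); power = Φ(0.1625/SE − 1.96).

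For R² = 0, SE = 0.5 × 0.1390 = 0.0695, 0.1625/0.0695 = 2.338, and power = Φ(0.378) = 65%.

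| R² | SE | Power |
|---|---|---|
| 0 | 0.0695 | 65% |
| 5% | 0.0677 | 67% |
| 10% | 0.0659 | 69% |
| 20% | 0.0622 | 74% |
| 30% | 0.0582 | 80% |
| 40% | 0.0538 | 86% |

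The standard error falls by 1 − √(1 − R²), which is 2.5% at R² = 5% and 22.5% at R² = 40%.

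If all 248 are analysed (124 per arm), SE = 0.5 × √(2/124) = 0.0635 and unadjusted power is Φ(2.559 − 1.96) = 73%.

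**Step 5: what the choice of test alone costs.** For the same 15% reduction at log-SD 0.4, 0.5 and 0.6, simulated power was 80%, 60% and 42% for the t-test, 80%, 63% and 46% for Wilcoxon, and 82%, 64% and 47% for an unadjusted log-scale analysis. Wilcoxon gives up only 1 to 2 points against the log scale.

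**The case against.** The strongest reply is that the rule is harmless in practice. If procedure times are clearly skewed, it nearly always selects Wilcoxon, so the question asked hardly varies with the data. Wilcoxon loses almost nothing in power, and an unadjusted comparison in a randomised trial is valid. Medians or a Hodges-Lehmann shift in minutes could accompany the rank test. No effect measure is stated for any outcome, so that gap is general. Duration is secondary.

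Most of this stands. What it leaves is that the plan commits to none of those estimates, and that nothing in the documents fixes how normality will be judged or how skewed the times will be.

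A reader might infer that the open criterion raises the false-positive rate. Running both tests and taking the smaller p-value would give 6.7% to 7.7% in simulation. The plan does not permit that, because it ties the test to normality. The figure describes a breach of the rule and not the rule itself.

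A reader might also infer that a large gain in precision is being thrown away. The documents do not say how strongly indication predicts duration. The sentence naming it a predictor directly follows an outcome list without duration. The same section warns that the underlying cause may differ from the suspected pre-procedure diagnosis, which would weaken it as a covariate.

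**Conclusion.** The point holds as one of clarity and efficiency for a secondary outcome. The quantity estimated for duration depends on an unspecified check of unblinded data, no estimate or interval is promised, and a covariate recorded before randomisation is left out. Type I error stays near 5% under the stated rule with the assumed criterion, and there is no bias from omitting indication. Success of the trial is defined on cannulation, so the primary conclusion is untouched.

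Practically all the recoverable power comes from adjustment and very little from the choice of test. The gain is about 2 to 21 percentage points (65% to 67–86%), resting on log-normal times, an assumed log-SD of 0.5, a 15% reduction, 207 analysed and R² between 5% and 40%. At the lower end of that range it is negligible. The case for one prespecified effect measure does not depend on R².

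**What to change.** Replace the normality rule with one analysis fixed in advance: a linear model of log(duration) on arm and pre-procedure indication, using the categories recorded before randomisation. Leave fellow involvement out, since the Study Calendar section records it after the procedure. Report the ratio of geometric means with a 95% interval, together with the difference in mean minutes and its 95% interval (by bootstrap, for example). The second estimate is needed because a ratio of geometric means is not itself time saved. Keep the Wilcoxon test only as a sensitivity analysis.

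This takes about two sentences in the Statistical Analysis section and no new data. The drawbacks are that clinicians will need a line explaining the ratio, and that the gain in precision may be small if indication predicts duration weakly.
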